3 TRIAL OBJECTIVES, ENDPOINTS AND ESTIMANDS

3.1 Primary Objective + Associated Endpoint and Estimand

| Primary Objective | Primary Endpoint |
|---------------------------------------|--|
| To evaluate efficacy of the procedure | Improvement of PROMs (KOOS, IKDC, VAS Pain Score) 2 and 5 years after surgery compared to scores of the non-operated group and compared to pre-surgery scores. |

Primary Estimand (Variable): Difference in PROMs after 2 and 5 years

Endpoint: 2 and 5 years after surgery/enrollment, or progression to TKA

Treatment: varies with the group chosen by the patient (operated or not operated)

Population: male and female patients between 18 and 60 years

Intercurrent event: progression of osteoarthritis up to TKA, lost to follow up, premature death, the patient wishes to change to the operated group after a certain time (The process: progression of osteoarthritis is very slow. It will be very unlikely that more than 1 patient wants to change to the operated group within the 5 years of the trial. The same is true for progression to TKA. The possibility to change later in the operated group will take off the pressure from the patient to make the “wrong” decision now.)

Population-level summary: The primary objective is to compare the PROM change from baseline between the operated and non-operated group after 2 and 5 years. The difference in obtained PROMS will be evaluated.

Estimand Description: The Estimand are the Difference in PROMs. This includes specific knee scores (IKDC, KOOS) and the VAS-Pain Score. IKDC and KOOS have values between 0 and 100 and the higher they are as better the function of the knee. The VAS Pain Score has values between 0 and 10 and the higher the score the higher the pain.

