4 TRIAL DESIGN

4.1 Description of Trial Design

Description of Intervention Model

This investigator initiated; low intervention trial is performed with 2 groups. The intervention group is the group of patients who will be operated. The control group are the patients not willing to be operated. Due to the incidence of patients with partial meniscal loss in the last years in the private praxis of the principal investigator 30 patients in the operated group and 10 patients in the non-operated group will be recruited within 2 years of recruitment. The study will be performed to prove patient safety and efficacy of the procedure. The process of progression of osteoarthritis is very slow. It will be very unlikely that more than 1 patient will be in this situation and wants to change to the operated group within the 5 years of the trial. The same is true for progression to TKA. The possibility to change later in the operated group will take off the pressure from the patient to make the “wrong” decision now.

Description of Trial Duration

The total trial duration will be 7 years. The recruitment period will be 2 years. Follow-up is 5 years. Depending on, if the patient will be operated or not, the time until surgery will add on these 5 years. The substance used (human cancellous bone) does not have a dose. It will be used in various dimensions.

Method of Assignment to Trial Intervention

This is a single centre trial. The initiator of the trial will perform the trial on its own. Due to the small number of patients included, the investigator will perform all visits on its own. There is no randomization. The patient decides if he/she will be operated or not. There is no blinding. A clinical monitor will perform data monitoring. There are no plans for a data monitoring committee due to the small number of patients and small number of data recorded. Bias is minimized by investigating the MRI images after a standardized protocol. The PROMs are filled in by the patient without the help of the investigator. The analysis will be performed by the investigator using statistical software. Patients from the non-operated group can transition to the operated group at any time. There are no rules for transition.

An interim analysis is planned after 2 years. See details in section 9.7

There will be no sample collection during the trial. In the moment there is no extension of the trial over the 5 years planned.

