7.1.2 Temporary Discontinuation or Interruption of Trial Intervention

This is an orthopedic trial. The surgery is the start point and after the surgery there are no treatments. There are only follow-up visits, which include an MRI and 3 questionnaires (IKDC, KOOS, CRF)

If the patient cannot attend a post-surgical visit at the time envisaged it is possible to do the visit later/earlier. For this there are time ranges given which is as follows:

- U1: at the end of hospital stay (only for operated patients)
- U2: 6 weeks after surgery (\pm 4 days, only for operated patients)
- U3: 6 months after surgery (\pm 1 months, for operated patients, for non-operated patients only PROMs)
- U4: 12 months after surgery (\pm 1 months, for operated patients, for non-operated patients only PROMs)
- U5: 24 months after surgery (\pm 1 months)
- U6: 5 years after surgery (\pm 3 months)

If for any reason this time slots cannot be used by the patient e.g. because of a pandemic or another major event, then the next time slot will be used.

Thus, a temporary discontinuation of the trial is not a problem, because no treatment occurs after surgery, but should be avoided.

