9 STATISTICAL CONSIDERATIONS

Data analysis complies with ICH E9 Guideline and ICH E9(R1) Guideline. This clinical trial is to confirm patient safety and efficiency of the procedure.

For this reason, as primary objective PROMs (IKDC, KOOS and VAS-pain score) will be evaluated before surgery/at the beginning of the trial and then starting at 6 months after surgery/beginning of the trial for the operated or non-operated group, respectively. The evaluation will be performed also after 12 and 24 months and after 5 years. A primary analysis will be performed 2 years after surgery/start of the trial.

At the beginning of the trial and prior to operation demographic and baseline data will be collected and summarized for both groups.

For safety, there will be an evaluation of complications, AE, SAE and SUSARs at each follow-up visit (at the end of the hospital stay, after 6 weeks, after 6, 12, 24, months and after 5 years, for the operated group). The number of AE, SAE and SUSARs will be recorded and evaluated at each visit. MRI evaluation starts at the follow-up visit 6 weeks after surgery for the operated group and 24 months after the start of the trial for the non-operated group. The evaluation of the MRI will be performed after a modified graduation of Genovese et al. [32]. Additionally, there will be the meniscal size evaluated and if there is an extrusion of the meniscus and how big the extrusion is. There will be a Kaplan-Meier-time to event curve for both groups regarding progression of osteoarthritis up to TKA. The analysis will be conducted on all participant data after 2 years and after 5 years.

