9.2.3 Handling of Missing Data

If the patient withdraws his consent, data up to this date will be used for the analysis. The last observation carried out will be the end point. Patient will be reported as withdrawn.

Patients are not randomized and do not have therapy after surgery, they just have follow-up visits. There will be the full analysis set model for the analysis, thus all data from patients will be reported, which were

enrolled. If a patient is lost to follow up, the patient will be reported as this.

For patients with progressing of osteoarthritis up to TKA, they will be recorded as failed. Data up to the event will be analyzed.

There will be no assumptions made for missing data. Data from last observation will be analysed. A drop-out of 20% is accepted in orthopedic trials.

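### Patients who miss the 24-month window have no slot until the 5-year visit, so 2-year primary PROMs that could be obtained are not collected; after the 5-year visit there is no fallback

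*Protocol*

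**What the plan says.** Section 7.1.2 allows visits to be done earlier or later within listed ranges. "U5: 24 months after surgery" carries a range of plus or minus 1 month, and "U6: 5 years after surgery" carries plus or minus 3 months; section 1.3 gives the same ranges. If a range cannot be used, whatever the reason, "then the next time slot will be used". The section concludes that a temporary interruption is not a problem, though it should be avoided.

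These two visits carry the primary data. Section 3.1: "The primary objective is to compare the PROM change from baseline between the operated and non-operated group after 2 and 5 years". Section 9: "A primary analysis will be performed 2 years after surgery/start of the trial". Section 9.7 adds that the 2-year result will be published.

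On how the scores are obtained, section 4.1 says "The PROMs are filled in by the patient without the help of the investigator". On missing values, section 9.2.3 says that no assumptions will be made and then: "Data from last observation will be analysed". Section 9.3, on the secondary objectives, says that missing data will not be estimated. No section provides for a late or remote questionnaire at U5 or U6.

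**The concern.** The fallback for the visit that feeds the primary analysis is a visit about three years later. Someone who is away for the two months of the U5 window and returns the next week is, under the rule as written, not asked for the 2-year scores. The protocol itself does not regard an earlier score as a substitute: section 4.2 says that the result can be judged only from 2 years on, and that graft shrinkage may occur up to that time. Section 7.3 expects young, active patients to move away for work or private reasons. Such patients may be unable to attend and yet able to fill in a form.

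At stake is the completeness and timing of the primary scores in a trial with only 10 controls. A statistical analysis plan could widen an analysis window, but it could not recover a questionnaire that was never requested.

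**Working it through.** **1. Visit calendar** (sections 1.3 and 7.1.2)

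- U4: 12 ± 1 months, so months 11 to 13.
- U5: 24 ± 1 months, so months 23 to 25.
- U6: 60 ± 3 months, so months 57 to 63.
- Time without any slot between U5 and U6: 57 − 25 = 32 months. The nominal visits are 60 − 24 = 36 months apart.
- Patient first available in month 26: earliest next slot is 57 − 26 = 31 months later.
- Patient who misses month 63: no later slot exists, so the rule gives no instruction for the second primary time point.

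**2. What then enters the 2-year comparison**

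The text supports two readings.

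- *Last value used.* Sections 9.2.2 and 9.2.3 analyse the last observation. The patient is represented by U4 or something earlier, nominally 24 − 12 = 12 months too early. A month-26 questionnaire would have been 26 − 24 = 2 months late.
- *Patient absent.* The last-observation wording stands among rules for withdrawal, loss to follow-up and progression to knee replacement. A missed visit is not among the intercurrent events in section 9.2.2. With no assumptions made for missing data, a patient who is still in the trial may simply have no 2-year value.

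**3. Weight of one patient** (section 9.8: 30 operated and 10 non-operated; 24 and 8 after 20% loss)

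- Non-operated: 1/10 = 10%; after the planned loss 1/8 = 12.5%.
- Operated: 1/30 = 3.3%; after the planned loss 1/24 = 4.2%.

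**4. Is the stated power threatened?**

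Two-sided unpaired t-test, noncentral t distribution, noncentrality = d × √(n₁n₂/(n₁+n₂)), degrees of freedom n₁+n₂−2, with d = 2.0 from section 9.8.

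The protocol's own figures first:

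- 30/10, alpha 0.00655: noncentrality 2.0 × √7.5 = 5.48; power 0.9935 (stated 0.993).
- 24/8, alpha 0.014: noncentrality 2.0 × √6 = 4.90; power 0.9857 (stated 0.985).

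Both reproduce. Next, further losses on top of 24/8. The numbers lost are assumptions, because the protocol gives none.

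| Operated / non-operated | d = 2.0, alpha 0.014 | d = 2.0, alpha 0.05 | d = 1.0 (assumed), alpha 0.05 |
|---|---|---|---|
| 24 / 8 | 0.9857 | 0.9973 | 0.6593 |
| 22 / 7 | 0.9704 | 0.9934 | 0.6033 |
| 19 / 6 | 0.9365 | 0.9833 | 0.5342 |

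At the protocol's effect size, power stays above 0.93 throughout. The last column shows only that this comfort depends on d = 2.0.

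**The case against.** The strongest reply is that a window of plus or minus 1 month is a legitimate design choice, that the protocol already allows movement within it and discourages interruption, and that nobody knows how many patients would miss it. That stands, and it limits the weight of the point. It does not answer the fallback: the question is what happens after month 25, and the only instruction given is to go to the next slot. In a list of dated visits that most naturally means the next listed visit.

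Three stronger readings are tempting, and the documents do not support them.

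- *That late data are thrown away.* No section orders a late questionnaire to be deleted. The rule leads to scores not being collected.
- *That the 12-month score certainly replaces the 2-year score.* This is one of the two readings in step 2, and the text does not settle it.
- *That precision falls by a known amount.* A reader might take the protocol's 20% and compute √(1/24+1/8)/√(1/30+1/10) = 1.118, a 12% larger standard error, or 4% for one missing control. But the 20% in sections 6.7, 9.8 and 11.1 is the allowance for total drop-out, already planned for; it is not a rate of missed windows. The calculation also presumes that these patients leave the analysis. If the last value is used, the group sizes do not change and the cost is bias from a mistimed score.

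It is also fair to say that sections 8.11 and 11.1 place questionnaire completion at the visit. Remote return is therefore a proposal, not something that the protocol already provides. It is a modest step, since patients complete the forms unaided and section 7.1.2 already has questionnaire-only assessments for non-operated patients at 6 and 12 months.

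**Conclusion.** The point holds as a fault in a data-collection rule. As written, section 7.1.2 leaves 32 months without a slot after the U5 window and nothing after the U6 window, so primary scores that could be had are forgone. The consequence is a missing 2-year value or one from 12 months or earlier, and the text leaves open which. One affected control is 10% to 12.5% of that group's 2-year data. The frequency is unknown, the size of any bias cannot be calculated from the documents, and the stated power is not threatened at d = 2.0. The conclusion rests on reading the next slot as the next listed visit. It is a change worth making because it is cheap and cannot be made once the data have been missed.

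**What to change.** For the questionnaires at U5 and U6, replace the next-slot rule with the following.

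- If the visit window is missed, obtain KOOS, IKDC and VAS pain as soon as possible, in person, by post or electronically, up to a bound fixed in advance: for example month 30 for U5, with a similarly bounded extension for U6.
- Record the actual completion date and use the value as that visit's outcome.
- Add a sensitivity analysis restricted to values obtained inside the original windows.

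The bound matters. Assigning each score to the nearest planned visit would accept anything from month (12 + 24)/2 = 18 to month (24 + 60)/2 = 42 as the 2-year outcome. That is too wide for an open trial whose investigator also does the analysis.

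Cost: a change of wording and a form that can be mailed or sent electronically. The price is somewhat more spread in assessment times and a possible effect of the mode of completion; the recorded dates and the in-window analysis allow the effect of timing to be examined.

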7.1.3 Rechallenge

Because the treatment is finished after the surgery, there is no re-challenge possible for patients in the operated group. Patients from the non-operated group can change to the operated group, but this is than no rechallenge, but the start of the trial as described under 1.2 Trial Scheme.

7.2 Participant Withdrawal from the Trial

This is an orthopedic trial. The surgery is the start point and after the surgery there is no further treatment. There are only follow-up visits, which include an MRI and 3 questionnaires (IKDC, KOOS, CRF). If a participant withdraws his informed consent. If the patient is not compliant with the restrictions for rehabilitation after surgery (as described under 5.5.3), the investigator has the right to withdraw the patient from the trial. Data are used until the withdrawal.

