5.5.3 Physical Activity

Physical activity is restricted for the patients having an operation as follows: Rehabilitation consist of 5 weeks partial weight bearing, range of motion will be restricted for the first 3 weeks to 30 °flexion, 4th week 60 °, 5th week 90 °, then full range of motion exercises were allowed. Jogging is not allowed for 4 months and contact sport only after 6 months.

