6.6.3 Blinding and Unblinding

There is no blinding

Emergency Unblinding: Because there is no blinding there is no need for emergency unblinding.

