6.8.2 Permitted Concomitant Therapy

Every other therapy is permitted during the trial.

Rescue Therapy

There is no rescue therapy. The patient who progress to osteoarthritis or TKA would be excluded from data interpretation but would remain in the trial as the full analysis set principle is followed. This patient would be counted as failed treatment.

A withdrawal from the trial by the patient (after surgery) will only affect the follow-up data. Withdrawal before surgery will not generate follow-up data, but patient will still be left in the study due to the full analysis set principle. This does not lead to temporary discontinuation of the study.

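### Section 7.2 lets the unblinded investigator end an operated patient's follow-up for poor rehabilitation compliance, a one-arm, discretionary loss of 2- and 5-year outcomes that can bias the comparison in a direction the protocol does not fix

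*Protocol*

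**What the plan says.** Section 7.2 provides that if a patient does not keep to the rehabilitation restrictions of 5.5.3, "the investigator has the right to withdraw the patient from the trial. Data are used until the withdrawal". The same section states that after surgery only follow-up visits remain.

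The restrictions are in 5.5.3, which opens "Physical activity is restricted for the patients having an operation as follows" and ends with "Jogging is not allowed for 4 months and contact sport only after 6 months". They therefore concern one arm and run up to 6 months after surgery.

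On who decides: 6.6.3 states "There is no blinding", and 4.1 says that "the investigator will perform all visits on its own". Section 4.1 also gives the analysis to the investigator and plans no data monitoring committee. Section 4.4 says investigator and sponsor are the same person.

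Section 7.1.1 lists the grounds on which a single patient leaves: withdrawn consent, loss to follow-up, death, progression to TKA, and a change to the operated group. Sections 3.1 and 9.2.2 list the intercurrent events. Rehabilitation non-compliance is in none of these lists.

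On handling, 9.2.2 and 9.2.3 bring the last observation into the analysis. Section 9.2.3 also says that nothing is assumed about missing data, and 9.3 says that missing data are not estimated. The full analysis set is the stated principle (5.6, 9.1, 9.2.3).

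**The concern.** The right arises after treatment, can be used in one arm only, and has no stated criterion. It is held by someone who knows the treatment, has seen the patient's course and will run the analysis. A patient who resumes activity too early may also be one whose knee does badly. The protocol does not say so, but it is plausible enough that such losses cannot be taken as unrelated to outcome.

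At stake are the primary comparison at 2 and 5 years and the later failures, reoperations, complications and MRI findings of these patients. A statistical analysis plan can state how to handle their missing values, but it cannot recover outcomes that the protocol allowed not to be collected. Because the ground is not an intercurrent event, the protocol also fixes no strategy for it.

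**Working it through.** **The plan's own figures.** For the two-sided independent t-test with effect size 2.0 (9.8), the noncentral t gives power 0.9935 for 30/10 at alpha 0.00655 (stated 0.993) and 0.9857 for 24/8 at alpha 0.014 (stated 0.985). Both reproduce. A few withdrawals do not threaten power as planned, so the question is bias.

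**Inputs from the protocol.** Operated arm 30. Expected IKDC 55 before and 84 after surgery, a gain of 29; KOOS 46 and 86, a gain of 40 (9.8). Expected withdrawal at most 5% (11.1): 5% of 30 is 1.5 patients, and 5% of all 40 is 2 if all fall in the operated arm.

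**Assumptions.** The expected gain M applies to patients who are not withdrawn. Withdrawn patients have a true mean gain c, which the protocol does not give; I take c = 10 and then the range from 0 to M. The number withdrawn, k, is also assumed. Withdrawal comes before the first post-operative PROM.

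**Formulas.** True operated mean gain = [(30 − k)M + kc]/30.
- Withdrawn patients omitted: the observed mean is M, so bias = (k/30)(M − c).
- Baseline carried forward: the observed mean is (30 − k)M/30, so bias = −(k/30)c.

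**IKDC, M = 29, c = 10** (positive favours surgery):

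| k of 30 | omitted: k × 19/30 | baseline carried forward: −k × 10/30 |
|---|---|---|
| 1.5 | +0.95 | −0.5 |
| 2 | +1.27 | −0.67 |
| 3 | +1.9 | −1.0 |
| 6 | +3.8 | −2.0 |

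Check for k = 3: the true mean is (27 × 29 + 3 × 10)/30 = 27.1. Omission gives 29.0; carrying baseline forward gives 783/30 = 26.1.

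**Range over c from 0 to M.** IKDC, omitted: 0 to +1.9 for k = 2 and 0 to +5.8 for k = 6. Carried forward: the same sizes with the opposite sign. KOOS (M = 40): 0 to 2.7 for k = 2 and 0 to 8.0 for k = 6, with the same pattern of signs. Under carry-forward of baseline, the bias favours surgery only if withdrawn patients end below baseline.

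**Which observation would be last.** Section 9 starts the PROMs at 6 months. The schedule in 1.3, as its columns read, marks the scores from the 12-month visit. Table 1 in 6.1 puts them at every follow-up visit, including discharge and 6 weeks. On the first two, a patient withdrawn during the restriction period would usually have only a baseline score. On the third, an early post-operative score may be carried forward, and its relation to the 2-year value is unknown.

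**Events.** After withdrawal, scheduled collection stops, so a later failure may go uncounted. Illustration with assumed counts: 7/30 = 23.3% exceeds the 20% that triggers a benefit-risk review (7.4, 9.7). If two of the seven are withdrawn before failing, the rate is 5/30 = 16.7%, or 5/28 = 17.9% if they leave the denominator, and no review follows.

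**The case against.** The strongest reply is that this is loss of later follow-up and not removal from the data. Data up to withdrawal are kept, and 9.2.3 reports all enrolled patients. That stands.

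A reader might infer a contradiction with the full analysis set from the rescue-therapy text under 6.8.2, where the "patient will still be left in the study due to the full analysis set principle". That sentence concerns withdrawal before surgery. The sentence before it says that a patient's own withdrawal after surgery affects only the follow-up data, which agrees with 7.2. The text does not show a contradiction. The gap is that 7.2 adds a ground for leaving that 7.1.1, 9.2.2 and 9.2.3 do not cover.

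A reader might also infer that all controls stay in. They do not: under 7.1.1 controls can leave through withdrawn consent, loss to follow-up, death, TKA or a change to surgery. Only the rehabilitation ground is one-sided.

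Numbers are expected to be small: 6.7 expects high compliance with the activity restrictions and 11.1 at most 5% withdrawal. This limits the likely size, but these are expectations and do not constrain the right itself. The event illustration is remote if failure means only TKA, since 4.1 expects no more than one such patient and 11.1 puts the chance at 2.5%.

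An independent clinical monitor is planned (8.3), but the protocol gives that role no part in the decision to withdraw.

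**Conclusion.** The point holds as a weakness of the design. Section 7.2 creates a discretionary loss of outcomes after treatment that can arise only in the operated arm, with no threshold and no stated handling. It can bias the 2- and 5-year comparison.

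The tempting stronger conclusion is that it biases the result towards surgery. For the PROMs the protocol does not support that. It requires both that withdrawn patients do worse and that they are omitted; the last-observation wording in 9.2.2 and 9.2.3 may instead carry baseline forward and reverse the sign. At the protocol's own withdrawal rate and an assumed gain of 10, the IKDC bias lies between about −0.7 and +1.3 points, against an expected gain of 29. At 6 of 30 it lies between −2.0 and +3.8. For failures, reoperations and other later events, under-counting in the operated arm is possible, but its size cannot be set from the protocol.

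These sizes rest on the assumed k and c and on withdrawal before any post-operative PROM. The likely effect is modest, but it is cheap to prevent and cannot be repaired once the visits have been missed.

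**What to change.** 1. In 7.2, remove rehabilitation non-compliance as a ground for ending trial follow-up after surgery.
2. Record non-compliance in the CRF, with date and nature. Keep the patient in all planned visits and in the full analysis set.
3. Add it to the intercurrent events in 3.1 and 9.2.2, to be analysed regardless of compliance. If wanted, add a sensitivity analysis in compliant patients, labelled as such.
4. Reconcile 7.2 with 7.1.1, 9.2.2 and 9.2.3, so that the grounds for leaving and the handling of data after each are the same throughout.
5. Leave withdrawal of consent, and the medical withdrawal before surgery in 4.4 and 10.5, as they are.

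The cost is wording, a CRF item and a few visits that are already planned. The observed effect may turn out slightly smaller. No change to the rehabilitation restrictions is implied.
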